6.4 Pubertal stage

Size of the testis and hairiness will be registered at visit 1, 7, 8, 9 and 10.

6.5 Signs of masculinization

Signs of masculinization will be evaluated by the study nurse at visit 8 and 10 after 6 and 12 months of hormone replacement. Testis size, pubic and axillary hair, growth and weight gain will be evaluated.

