Endpoints and variables

The primary endpoint in group I (boys with absent puberty) will be increase in blood LH after GnRH test. Testis size ≥ 8 mL will be the primary endpoint for group II (boys with delayed puberty).

Secondary endpoints are increase in testis size from baseline to 1 year (group I), serum testosterone levels during treatment with Testoviron Depot® and Nebido®, signs of masculinization from baseline to 3, 6 and 12 months, body growth, hair growth measured as tanner stage and inspection of axillaries hair, deepening of voice, gender identity and health-related quality of life.

TABLE OF CONTENTS	PAGE
PROTOCOL SYNOPSIS	2
TABLE OF CONTENTS	4
LIST OF ABBREVIATIONS AND DEFINITION OF TERMS.....	7
1. INTRODUCTION	9
1.1 Background	9
1.2 Rationale for conducting this study	10
1.3 Research hypothesis.....	11
1.4 Benefit/risk and ethical assessment.....	11
1.5 Ethical assessment	11
2. STUDY OBJECTIVES AND ENDPOINTS.....	12
2.1 Primary objective	12
2.1.1 Primary endpoint(s)	12
2.2 Secondary objective(s).....	12
2.3 Exploratory variables	12
3. STUDY DESIGN AND PROCEDURES	12
3.1 Overall study design and flow chart	12
3.1.1 Stopping criteria.....	15
3.1.1.1 Stopping criteria for dose continuation.....	15
3.2 Rationale for study design, doses and control groups.....	15
4. SUBJECT POPULATION.....	16
4.1 Inclusion criteria Group I (absent puberty).....	16
4.2 Inclusion criteria Group II (delayed puberty)	17
4.3 Exclusion criteria	17
4.4 Subject enrolment and randomization	18
4.5 Restrictions during the study	18
4.6 Withdrawal of subjects and study stop	18
4.6.1 Premature termination of the study.....	18
5. TREATMENTS	19
5.1.1 Doses and treatment regimens	19
5.1.2 Labelling	20
5.1.3 Storage	20
5.2 Concomitant medication and post-study treatment(s)	20

5.3	Treatment compliance.....	20
5.3.1	Accountability.....	21
6.	STUDY MEASUREMENTS AND VARIABLES	21
6.1	Screening and demography.....	21
6.1.1	Methods of assessments.....	21
6.1.2	Post-study.....	21
6.2	Bone age.....	22
6.3	LHRH-test.....	22
6.4	Pubertal stage.....	22
6.5	Signs of masculinization	22
6.6	Blood sampling.....	22
6.6.1	Study-specific blood samples	22
6.6.1.1	Haemoglobin (Hb)	23
6.6.1.2	LH and FSH	23
6.6.1.3	DHEAS	23
6.6.1.4	Testosterone and Estrogen.....	23
6.6.1.5	SHBG, AMH, InhibinB	23
6.6.1.6	Mass spectrometric analysis of steroids.....	23
6.6.2	Questionnaires.....	23
6.6.2.1	Standardize procedures for administration of questionnaires.....	23
6.6.2.2	KIDSCREEN	24
6.6.2.3	Jag Tycker Jag Är	24

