2.2 Secondary objective(s)

- Testis size (mL) in group I from baseline to 1 year (group I)
- Serum testosterone levels during treatment with Testoviron Depot® and Nebido®.
- Signs of masculinization from baseline to 3, 6 and 12 months (Body growth, hair growth measured as tanner stage and inspection of axillaries hair, deepening of voice, gender identity)
- Health-related Quality of life (KIDSCREEN, JTJÄ)

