II) Boys with delayed/slow progress of puberty (testis 4-6 mL and morning testosterone less than 4 nM) will be randomized to receive either 1) Testoviron Depot® (SoC) 75 mg i.m. injection once a month (SoC) or 2) Nebido® one injection of 250 mg at start and after 3 month. The treatment will continue for 6 months, dose adjustments will be possible after the first 4 patients on Nebido® (250 mg) for the rest of the study. The aim for the Nebido® treatment is to have morning testosterone levels in the lower range of mid puberty (4-9 nmol/L). An interim analysis has to be done after the first 5 patients and thereafter keep or adjust the dose (see appendix D for adjustment of the Nebido® dose for group II). The treatment will be evaluated after 6 month on development of masculinization and on spontaneous start of puberty after 12 months.

Figure 1 and Table 1 show the study overview and activities.

Figure 1a Study design Group I (absence of puberty)

[figure not shown]

Figure 1b Study design Group II (delayed puberty)

[figure not shown]

Table 1 Study activities

	Visit 1	Visit 2	Visit 3	Visit 4	Visit 5	Visit 6	Visit 7	Visit 8	Visit 9*	Visit 10
	Pre-	0	2 days	7 days	1 month	2 months	3 months	6 months	9* months	12 months
Informed consent	X									
Demography	X									
Medical history	X									
Nicotine use	X									
Weight, height	X						X	X	X	X
Pulse, blood pressure	X									
Physical exam	X									
Bone-age	X									
LHRH test	X									X*
Pubertal stage	X						X	X	X	X
HQOL	X							X		X
Hb, liver enzymes	X						X	X		X
LH, FSH	X	X		X*	X		X	X	X	X
DHEAS,		X						X		X
Incl/excl criteria		X								
Study drug		X								
Testosterone, estradiol		X	X	X	X	X	X	X		X

SHBG, AMH, InhibinB		X			X			X		X
Signs of masculinization								X		X
Plasma for masspektometri of steroids	X							X		X
Adverse events	X	X	X	X	X	X	X	X	X	X
Serious Adverse event recording	X	---	---	---	---	---	---	---	---	---

*Visit 9: Group I only

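### Signs of masculinization are defined as change from baseline at 3, 6 and 12 months but scheduled only at 6 and 12: voice and gender identity are never measured, and axillary hair probably lacks a baseline

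*SAP*

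**What the plan says.** Section 2.2 lists as a secondary objective "Signs of masculinization from baseline to 3, 6 and 12 months". In brackets it names the components: body growth, Tanner hair stage, and then "inspection of axillaries hair, deepening of voice, gender identity". The synopsis repeats the time frame, "signs of masculinization from baseline to 3, 6 and 12 months", and names the same items in a running list.

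Section 6.5 gives the assessment: "Signs of masculinization will be evaluated by the study nurse at visit 8 and 10 after 6 and 12 months of hormone replacement". Its items are: "Testis size, pubic and axillary hair, growth and weight gain will be evaluated". The Table 1 row "Signs of masculinization" is ticked under visit 8 (6 months) and visit 10 (12 months) and nowhere else.

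Two other parts of the schedule overlap with this endpoint. Section 6.4 says "Size of the testis and hairiness will be registered at visit 1, 7, 8, 9 and 10". Table 1 has weight and height at those same visits. Visit 9 is for Group I only.

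**The concern.** An endpoint defined as change from baseline needs a value before treatment and a value at each stated time point. The masculinization assessment itself has neither a baseline visit nor a month-3 visit. Two of the named components, "deepening of voice, gender identity", do not appear among the items that section 6.5 says will be evaluated, even at months 6 and 12.

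If the sites follow the plan exactly, part of a stated secondary endpoint cannot be reported. The endpoint carries some weight: section 3.1 makes masculinization one of the things on which treatment is evaluated in both groups. A starting value not recorded before the first injection cannot be recovered later.

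**Working it through.** The plan states no figure to reproduce. The check compares each component in section 2.2 with every place where the plan schedules a measurement.

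**Where a value could come from**
- Table 1, weight and height: visits 1, 7, 8, 9 and 10.
- Section 6.4 and Table 1, pubertal stage (testis size and hairiness): visits 1, 7, 8, 9 and 10.
- Section 6.5 and Table 1, signs of masculinization: visits 8 and 10.
- Section 6.1, pre-entry examination: its listed content does not name axillary hair, voice or gender identity. Table 1 has a physical examination at visit 1 only.
- Sections 6.6.2.2 and 6.6.2.3, the two questionnaires: neither description mentions gender identity.

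**Scheduled values by component**

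| Component (section 2.2) | Baseline | Month 3 | Month 6 | Month 12 |
|---|---|---|---|---|
| Body growth | yes | yes | yes | yes |
| Pubic hair (Tanner) | yes | yes | yes | yes |
| Axillary hair | probably not | probably not | yes | yes |
| Deepening of voice | no | no | no | no |
| Gender identity | no | no | no | no |

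The axillary row turns on what hairiness means in section 6.4, where the word is unqualified. Section 6.1 describes puberty stage at the pre-entry visit as testicular volume and pubic hairiness. Section 6.5 names pubic and axillary hair as separate items. Both point to section 6.4 meaning pubic hair.

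**Count of derivable changes**
- Defined: 5 components × 3 time points = 15 changes from baseline.
- Derivable, narrow reading of hairiness: growth 3 + pubic hair 3 = 6 of 15.
- Derivable, if hairiness includes axillary hair: 6 + 3 = 9 of 15.
- The remaining 6 (voice 3, gender identity 3) are not derivable on either reading.

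**The case against.** The strongest case against the point has four parts.

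1. *The endpoint is not lost.* A reader might infer that masculinization as a whole cannot be computed. The schedule does not support that: growth and pubic hair have values at baseline and months 3, 6 and 12 through other rows. This stands and limits the point to three components.

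2. *Axillary hair may be covered.* Section 6.4 is unqualified, and the narrower wording in section 6.1 describes only the pre-entry visit. This stands in part. The gap is probable, not certain, so it would be too strong to say that change in axillary hair can never be calculated. Wording that sites could read either way still needs settling, and the argument does not reach voice or gender identity.

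3. *Randomisation protects the comparison.* A reader might infer that, without a baseline, differences between arms at month 6 mix treatment effect with differences at entry. That would be confounding, and allocation here is randomised. A comparison of month-6 or month-12 status is unbiased in expectation, and chance imbalance is part of the sampling error. This stands.

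4. *Month 3 may be the slip.* Section 3.1 evaluates masculinization after 6 and 12 months in Group I and after 6 months in Group II, in line with section 6.5 and Table 1. Only the endpoint wording adds month 3. This stands, and it means the endpoint could be aligned to the schedule instead of the reverse. It does not supply the missing baseline or any measurement of voice and gender identity.

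The weight of the point is also limited: this is one secondary objective in a study that section 8 calls hypothesis-generating.

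**Conclusion.** The plan contradicts itself. The endpoint in section 2.2 and the synopsis does not match section 6.5 and Table 1. As written, change from baseline cannot be derived at any time point for voice or gender identity, and most likely not for axillary hair. For voice and gender identity not even status at 6 or 12 months is available, because no visit and no method is named. This applies to all 70 boys.

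The loss is of within-boy change, and of the precision that baseline adjustment could add with 15 boys per arm in Group I and 20 in Group II. The document gives no baseline data from which to quantify that precision. There is no bias in the randomised comparison, and neither primary endpoint is affected.

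The axillary-hair part assumes that hairiness in section 6.4 means pubic hair. The voice and gender identity parts need no such assumption. The matter should be corrected, but it does not threaten the main conclusions of the trial.

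**What to change.** - Record axillary hair and a voice item with defined categories at visit 1, before treatment, and at visits 8 and 10.
- For month 3, choose one: add visit 7, when pubertal stage is already examined, or delete month 3 from the endpoint for these components.
- State in section 6.4 whether hairiness means pubic hair only.
- For gender identity, either name a measure and its visits, or delete it from section 2.2 and the synopsis.
- Align the synopsis, section 2.2, section 6.5 and Table 1 with whichever choice is made.

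The cost is a few CRF lines and slight extra examination time at existing visits, plus a protocol amendment with the approval that section 9.5 requires. Keeping gender identity costs more than the other items, since it adds a separate assessment in minors.

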6.6 Blood sampling

For each patient blood will be collected for safety screen (6.5.3) and for the assessment of biomarkers relevant for the objectives in the study.

Samples will be labelled individually with pre-printed labels marked with study code, subject number, media (blood, plasma), visit number and date.

6.6.1 Study-specific blood samples

Venous blood samples will be taken at all follow-up visits according to Table 1. Venous blood will be collected in EDTA tubes, heparinized tubes and plain serum tubes. Some samples will be centrifuged

as soon as possible, transferred into cryovial tubes and immediately frozen. Some samples will be analysed immediately in connection to the visit and some will be stored until later analysis.

Capillary blood will be accepted in those cases when venous blood is not possible to draw. Depending on type of analysis approximately 250-3000 µL will be needed for the various analysis.

6.6.1.1 Haemoglobin (Hb)

Whole blood in EDTA tubes will be used for analysis.

6.6.1.2 LH and FSH

Venous blood for analysis of LH and FSH will be drawn at visits 1, 2, 5, 7, 8, 9 and 10 and analyzed as soon as possible at the central laboratory at each hospital.

6.6.1.3 DHEAS

Venous blood (2.5 mL) for analysis of DHEAS will be drawn at visits 2, 8 and 10. It will be frozen and stored in -20° C for later analysis.

6.6.1.4 Testosterone and Estrogen

Venous blood for testosterone (2.5 mL) and estrogen (5 mL) analysis will be drawn at visits 2, 3, 4, 5, 6, 7, 8 and 10, centrifuged, frozen and sent to tillväxtlab at Drottning Silvias barn- och ungdomsjukhus; Sahlgrenska University/Östra, Göteborg and stored in -20° C for later analysis.

6.6.1.5 SHBG, AMH, InhibinB

Approximately 10 mL venous blood will be drawn at visits 2, 5, 8 and 10 and centrifuged. Serum will be used for the analysis of SHBG (2.5 mL), AMH (5 mL) and Inhibin B (2.5 mL) .

Blood for the AMH analysis will be centrifuged within 4 hours, frozen and stored in -20° C for later analysis.

6.6.1.6 Mass spectrometric analysis of steroids

Approximately 5 mL blood will be drawn at visit 1, 8 and 10 and analyzed for 16 specific steroids with a mass spectrometric method. The analysis will result in a steroid profile which will be possible to compare against clinical status and treatment outcomes.

6.6.2 Questionnaires

6.6.2.1 Standardize procedures for administration of questionnaires

The questionnaires will be filled in at the study site. The patients should be allowed to sit alone in a reasonable quiet environment to answer the questions. It will be emphasized that patients complete the questionnaires prior to clinical measurements and before meeting a doctor. Questionnaires should be answered by the patient herself alone, however, the nurse/assistant will be informed about helping the patients to complete the questionnaires if necessary, however without influencing the patients'

responses. Ensure the patient confidentiality. Study nurse/assistant should check the questionnaires for completeness. The principal investigator will assure that appropriate training relevant to the study is given.

6.6.2.2 KIDSCREEN

Kids screen for children and adolescents (8–17 years) is a generic health-related quality of life instrument for both healthy and sic children. It measures physical well-being, psychological, well-being, social support, peers and financial resources. It takes 15 minutes to fill in by the patients themselves.

6.6.2.3 Jag Tycker Jag Är

”Jag Tycker Jag Är” (“Jag tycker jag är” (JTJÄ) - is a measure of well-being and self-esteem with the domains of physical abilities, mental health, and relationships with others. It is available for both 6-10 year old children and 11-16 years adolescents. The JTJÄ has been widely used in clinical trials in the Västra Götaland region and in the childrens clinic at Queen Silvia Hospital/SU/Ö in particular).

6.6.3 Safety measurements and variables

Blood (10 ml) for laboratory safety screen (Table 2) in a fasting condition will be taken at pre-entry visit (Table 4).

Table 4 Blood and urine screen

Clinical Chemistry	Haematology
S-Creatinine	B-Haemoglobin (Hb)
S-Bilirubin	B-Platelet count
SP-Alkaline phosphatase (ALP)	B-Leukocytes, total count
SP-Alanine aminotransferase (ALAT)	B-Leukocytes diff.absolute count:
S -Aspartate aminotransferase (ASAT)	
S-Albumin	Urinanalyser
S-Potassium	U-Erythrocytes (U-Ery)
S-Calcium	U-Albumin (U-Alb)
S-Sodium	U-Glucose (U-Glu)
P-Glucose	
CRP	
P-Cholesterol total	
P-TG, HDL, LDL	

The blood samples will be analysed with routine methods at the Department of Clinical Chemistry, SU/Östra, Göteborg and NÄL, Nu-sjukvården and valid reference values of all routine analyses will be obtained. Laboratory values outside the reference limit suspected to be of any clinical significance will be repeated.

6.6.4 Volume of blood

The total volume of blood that will be drawn from each subject in this study is as follows:

Table 5 *Volume of blood (ml) to be drawn from each subject*

Assessment	Visit	Total
Safety	1, 7, 8, 10	40
LH, FSH	1, 2, 5, 7, 8, 9, 10	35
Testosterone, estradiol	2, 3, 4, 5, 6, 7, 8, 10	60
DHEAS	1, 8, 10	10
SHBG, AMH, inhibin B	2, 5, 8, 10	40
Total		185

Approximately 185 mL blood will be drawn from each subject during the entire study. Some of the blood will be immediately analysed and some of the samples will be frozen for later analyses unidentified at Tillväxtcentrum Göteborg.

6.7 Handling, storage and destruction of biological samples

The safety blood samples at visit 1 will be used up or disposed after analyses.

Study-specific blood samples will be analysed during and after finalized study. These samples will be reported to the Sahlgrenska University Hospital/Ö primary biobank and stored for a maximum time period of 15 years and used only as objected in this study protocol. Samples are coded and code keys will be kept by the care provider. The origin can be traced to the human from whom it was taken.

6.7.1 Withdrawal of informed consent for biological samples

If a subject withdraws consent to the use of biological samples donated the samples will be disposed/destroyed, if not already analysed and documented and the subject is withdrawn from further study participation.

The principle investigator ensures the central laboratory holding the samples is informed about the withdrawn consent immediately and that samples are disposed/destroyed and the action documented returned to the study site.

7. SAFETY

It is of the utmost importance that the principal investigator and all staff involved in the study are familiar with the content of this section. The principle investigator is responsible for safety surveillance and for ensuring that procedures and expertise are available to handle medical emergencies during the study. Further details on definitions is described in Appendix B.

In the case of a medical emergency the investigator may contact **[name] [name]** [contact] or at [name] or [name].

Physical examination, vital signs and safety blood screen will be made by the study physician at study start in order to document the health status of the subjects.

Adverse Events in the present study will be collected and registered from the time of signed informed consent throughout the treatment period including the follow-up period.

7.1.1 Definition of adverse events

An adverse event (AE) is the development of an undesirable medical condition or the deterioration of a pre-existing medical condition following or during exposure to a pharmaceutical product, whether or not considered causally related to the product. An undesirable medical condition can be symptoms, signs or abnormal results of an investigation.

In clinical studies, an AE can occur at any time, including run-in or washout periods, even if no study treatment has been administered.

The term AE is used to include both serious and non-serious AEs.

7.1.2 Definitions of serious adverse event

Serious AEs (SAEs) and discontinuations due to AEs must be collected and an assessment of causality of the SAE should be performed. An SAE is an experience that at any dose, during any study phase results in any of the following:

- Death
- A life-threatening experience
- In-patient hospitalization or prolongation of existing hospitalisation
- A persistent or significant disability or incapacity
- A congenital anomaly or birth defect
- Is an important medical event that may jeopardise the subject or may require medical intervention to prevent one of the outcomes listed above.

The following terms and definitions are used when assessing the causal relationship between each AE/SAE and the relevant trial product(s):

- Definite – There is no doubt that the incident is related
- Probably- Good reason and sufficient documentation to assume a causal relationship
- Possible- A causal relationship is conceivable and cannot be dismissed
- Unlikely- The event is most likely related to aetiology other than the trial product
- Unknown/Unclassifiable: a report suggesting an adverse event reaction, which cannot be judged because information is insufficient or contradictory and which cannot be supplemented or verified.

A **Suspected Unexpected Serious Adverse Reaction (SUSAR)** is a serious adverse reaction in subjects given a drug, which may or may not be dose related, but are unexpected, as they are not consistent with current safety information.

For further guidance on the definition of a SAE, see **Appendix B**.

7.1.3 Intensity rating

It is important to distinguish between serious and *severe* AEs. Severity is a measure of intensity whereas seriousness is defined by the criteria in Section 0. An AE of severe intensity need not necessarily be considered serious. The following terms are used for definitions for severity/intensity rating:

- None – No symptoms
- Mild - Transient symptoms; awareness of sign or symptom, but easily tolerated. No interference with the subject's daily activities
- Moderate - Marked symptoms; discomfort sufficient to cause interference with normal activities. Moderate interference with the subject's daily activities
- Severe - Considerable interference with the subject's daily activities; unacceptable, incapacitating. Inability to perform normal activities
- N/A Not Applicable

7.1.4 Reporting of serious adverse events (SAEs and SUSARs)

All SAEs have to be reported, whether or not considered causally related to the investigational product, or to the study procedure. All SAEs will be recorded on separate AE pages in the CRF. The SAE Data Form and fax confirmation sheet must be processed in accordance with guidelines on retention of records at the site.

The Ethics Committees and Regulatory Authorities must be informed by the sponsor; in this study the principle investigator, as soon as possible or within **7 days**. A supplemented detailed report must be sent within another **8 days**. The SAE Report Form will be used together with relevant supporting documentation (eg, ECG, laboratory results, autopsy report) and relevant CRF modules. The sponsor shall ensure that a SUSAR which is not fatal or life-threatening is reported within **15 days**.

All SUSARs have to be electronically registered in the EMEAs database. For the current study, the sponsor/principle investigator will delegate registration of SUSARs in the EudraVigilance database to the Swedish Medical Products Agency (Läkemedlesverket). The CIOMS form will be used and sent electronically to [contact].

The current reference safety information contained in FASS and homepage (Testoviron) will apply. All SAEs will be recorded in both subject hospital record and in the CRF.

Yearly safety summary reports including notifications of SAEs and SUSARs will be provided to the Ethics Committee and the MPA according to local regulations and guidelines

Follow-up of unresolved adverse events

Any AEs that are unresolved at the patient's last AE assessment in the study are followed up by the investigator for as long as medically indicated, but without further recording in the CRF.

